**Phase 1: Development and Training**

This phase includes conducting focus groups with tribal college smokers to obtain input on issues related to the internet based culturally-tailored program. Finalize development and assessment of interactive website. In addition, we will also develop strategies related to recruitment, study participation, and training of AI research staff. These smokers along with the Community Advisory Boards will also assist in finalizing and pilot testing the website and will play a strong role in the recruitment, retention, implementation, and dissemination of the proposed project.

**Focus Groups: Sampling Frame & Recruitment-** We plan six focus groups, three males and three female groups. We stratify by gender because, based on preliminary data, we learned that there are differences in smoking by gender. Because the Internet is a key aspect of our program, we need information from students to ensure we meet the needs of these participants. We plan 3 focus groups per stratum, but will assess saturation after conducting the focus groups and will

cease recruitment if our data are saturated. We plan for 10 participants in each focus group, for N=60.

***Development of Moderator's Guide:*** [name] will lead focus group moderator's guide development based on an examination of ANBL. Guide will be developed with Native team members and CABs and will be modified for each stratum. We will cover the following: previous experience with quit attempts, how smoking is similar to/different from cigarettes and traditional tobacco, and program development.

***Focus Group Procedures:*** Focus groups, lasting approximately 60 to 90 minutes, will be conducted at a variety of times to allow for participation of individuals with different schedules and will be audio-taped and transcribed verbatim. Focus groups will be moderated by ethnically and gender-matched research assistants who have been trained to conduct focus groups by [name], who will observe a minimum of 2 mock groups by each research assistant prior to allowing them to conduct groups. We have found that matching ethnicity when selecting focus group moderators is imperative to gaining richly detailed information. Prior to the start of the group, participants will provide written and verbal informed consent. Participants will receive a \$25 gift card and meal for their time and participation.

#### Digital Recordings:

All digital audio files will be housed on a secure network drive at the University of Kansas Medical Center after transcription and will be destroyed at study conclusion in 5 years. Transcripts and surveys will be kept in a locked file cabinet at the Center for American Indian Community Health. Transcripts will not be identified by name and no quotes will be attributed to any individual in any presentation of the data. The digital recordings will be labeled by unique participant identification numbers that will not be linked to any personal information. Data will be presented in an aggregate form, as well as with individual quotations, without identifying information.

***Focus Group Analysis:*** [name] will lead all analysis based on a CBPR approach developed by this research team. Text analysis will follow a grounded theory approach and will use techniques developed by the PI during analysis of qualitative data from previous work with community. In grounded theory, categories and concepts emerge from the text and are linked to formal theories. Using this approach will allow us to develop a more accurate theoretical framework and model of behavior. Analysis techniques follow a series of steps based in CBPR and ethnography and include five analysts, three coders and two reviewers of themes. Both scientists and community members are included in the coders and reviewers. Analytic coders read through the transcripts and inductively come up with topic areas. The coders meet and develop an initial code book based on these topics. Coders then reread transcripts, beginning deductive coding with the code book and including any inductive coding necessary to complete topic areas. Coders meet again to finalize the code book and then reread the transcripts, completing all deductive coding. Coders meet a third time to discuss themes, coming up with basic ideas about thematic statements, which are then drafted by the primary coder (scientist) and sent to the secondary coder (community member) for review. Coders meet a final time to reach a consensus on the thematic statements before they are sent to the emic and etic reviewers, who discuss the themes and come up with finalized statements that are brought to the full analytic team for consensus.

**Navigability of website:** We plan a series of 20 semi-structured interviews with AI smokers, 10 college male students and 10 female college students, to understand the navigability of the program website.

Because using our website is crucial to program success, we believe we need to test navigability with individuals who would be potential participants. Recruitment will follow a similar approach to recruitment for focus groups and other interviews. During each interview, participants will be asked to perform a series of activities on the website designed to test the difficulty each participant has in finding different information and interacting with the site (*see table - right*). Participants will also be asked a series of open-ended questions about the site and will be given additional time to “play” with the site and provide input.

In addition to our formal assessment, all members of the research team will try all navigation links within the site in an attempt to “break” it. Each time problems are found, they will be corrected. We have used this technique successfully in the past to develop multiple websites.

**Phase 2: Delivery of Interventions**

The objectives of this phase are to: (1) recruit and screen participants for eligibility into study; (2) randomize tribal college students into the two arms (**I-ANBL** or **I-FV**); and (3) implement interventions and follow-up. We will recruit and randomize 300 tribal college smokers into two groups – the culturally-tailored arm (**I-ANBL** + offered varenicline/bupropion/NRT) and the heart healthy arm (**I-FV** + offered varenicline/bupropion/NRT).

**Tribal College Student Recruitment**

As has been done previously, we will follow CBPR methods in that the leadership and administration will be involved in recruitment of smokers. We have a very strong track record

Possible Interview Tasks	
Finding Information	
	What you currently see is the home page for our quit smoking program. Please find the page that has facts about what smoking can do to your health and identify the different types of cancer that can be caused by smoking
	Please find the login for program participants. Once you find the login, I will give you a guest login so that you can see additional parts to the site that are meant for program participants.
	Within the participant site, please find the educational brochure for session 4: Traditional Use of Tobacco.
	Within the participant site, please find the announcement board for group 5. Are there any current announcements for this group?
	Within the participant site, please find the calendar of events for session 5. When is the next session?
Providing Information	
	What you currently see is the home page for our quit smoking program. Please find the page that allows you to submit your name for more information about the program and submit it.
	Please find the page that allows you to post a question to be answered by our staff and post something.
	Please complete the on-line survey about health effects of smoking and tell me what the graphic pie charts that pops up after you answer says about how others have answered.

with a few Tribal colleges on multiple initiatives to improve the health of both students and faculty at the tribal college. We will employ multiple recruitment strategies as we have done on previous projects and health activities. We will advertise on campus with both flyers and on their school website, in classrooms during both class and new student orientation, social media sites such as Facebook, and Native publications at the Tribal colleges. We have employed many graduates of tribal colleges who have established strong relationships with faculty and administration, which will provide consistency and a recruitment team well-experienced on study requirements. We will have no problem recruiting 242 smokers over 3 years of the study. To account for potential attrition, we will recruit a total of 300 smokers and assume a 20% attrition rate.

**Eligibility Requirements**

We will recruit a total of 300 tribal college students who are current smokers (smoked at least 1 cigarette in the past 30 days), at least 18 years of age, valid telephone number and email address, willing to be followed-up for 6 months, and willing to participate in all study components. Students who are planning to leave the university within next 6 months or who are medically ineligible after screening will be excluded from the study.

Annual number of students	Adjust for smoking prevalence * (40%)	Adjust down 50% for refusals	Adjust down 20% for no-show to enrollment	Targeted Total enrollment over 3 years
1,200	480	240 eligible	192 per year	300

We will recruit 14 students per month so that the process of medical screening for pharmacotherapy is not a burden on the on –the-ground physician and the research staff.

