Over the past 8 years, we developed a culturally-tailored, in-person, group-based adult smoking cessation program (All Nations Breath of Life – ANBL) using community-based participatory research methods. It takes into account the sacred role of tobacco among many American Indians and how culture affects smoking cessation among AIs. Preliminary data from our recent studies indicate that the internet may be more favorable and appropriate method for reaching younger and more mobile tribal college populations. Web interactivity, immediacy of feedback, and wider reach and accessibility will, we believe, contribute to greater success of the intervention. This proposal is an extension of our previous work. In this study, we will adapt and test a culturally tailored internet-based smoking cessation (**I-ANBL**) program based on ANBL, for a unique subset of the AI population: students enrolled in tribal colleges/universities.

**Primary Aim:** To test the effectiveness of a culturally-tailored internet-based smoking cessation intervention (**I-ANBL**) compared to an internet-based heart healthy diet (I-FV: fruit/vegetable) control condition in a randomized controlled trial with Tribal College students. Our hypothesis is that American Indian tribal college students randomized to the culturally-tailored smoking cessation arm will have significantly higher 7-day point prevalence abstinence (defined as no cigarettes in the past 7 days, biochemically verified) rates at 6 months than those receiving the heart healthy diet intervention.

Secondary Aims	Hypotheses
1. To test the effects of the intervention on intermediate smoking variables including number of cigarettes smoked and number of quit attempts at 6 months following randomization.	1. At 6 months following randomization, among those who continue to smoke, participants in the culturally-tailored (I-ANBL) condition will show a greater reduction in the number of cigarettes smoked than participants in the heart healthy diet arm ( I-FV ).
2. To compare differences between I-ANBL and I-FV in adherence rates to program participation at 6 months following randomization.	2. At 6 months following randomization, participants in the tailored I-ANBL group will have significantly higher adherence rates than smokers in the I-FV group.
Process Objectives	
1. To identify factors that enhance the dissemination aspects of the I-ANBL program.	

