*The results from this initial small pilot study of AI/AN smokers demonstrate our ability to recruit and successfully follow-up participants for a 6-month period to verify smoking abstinence. In addition, these results confirm smoking prevalence findings from other studies that AI/AN smokers are lighter smokers than white smokers in the U.S. Finally, the findings demonstrate preliminary efficacy of our ANBL program.*

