#### **Pilot Feasibility of ANBL in Urban and Reservation based Tribes in Kansas**

Our American Cancer Society (RSGT-06-260-01-CPPB: PI: [name]) funded grant is a 3 year pilot/feasibility study of ANBL with all program components. The ANBL program components include an initial individual session along with 8 weekly group sessions with individual telephone calls between the group sessions. During the previous pilot, we conducted the ANBL program with 5 weekly in person sessions and another version with 8 weekly in person sessions. The overwhelming preference from our participants was for the more intensive 8 weekly in-person group sessions. All of our participants expressed the need to maintain the group support and dynamics in order to maintain long term abstinence. As a result, we decided to implement the 8 session version rather than the smaller number of sessions. This larger pilot study started in 2006 and we have completed 10 groups of AI/AN smokers. In addition to the ANBL program, all participants were offered varenicline as a form of pharmacotherapy. In this pilot, we also added the use of motivational interviewing (MI) counseling throughout the individual phone sessions. Recruitment and retention (approximately 80%) has been very successful. All participants completed surveys for each group session and there have been no refusals among those in attendance. For the first time, we have also collected saliva samples from our participants at baseline, week 12 and 6 months to verify smoking status. The six month smoking abstinence rates are approximately 30% with ANBL in combination with varenicline. Our dropout rates for this larger feasibility pilot study have been between 15-20 % at 6 months.

***These results demonstrate our team's ability to recruit both urban and reservation based AI/AN smokers in the region. In addition, we have successfully shown our team's ability to maintain high recruitment and retention rates for the groups of smokers for the high intensity ANBL program. We have also successfully integrated the use of MI counseling during the individual phone calls and demonstrated acceptance in this population. Our current version of ANBL is more intense compared to the first version of the program. This increase in intensity is a result of participant and facilitator feedback that 5 in-person group sessions was***

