#### **IV. Inclusion/Exclusion Criteria**

##### **Eligibility**

The eligibility criteria listed below will be assessed at the recruitment visit.

Inclusion Criteria	Exclusion Criteria

 
◆ Age 18 years or older
 
◆ Currently enrolled at a Tribal college
 
◆ Have a valid telephone number and email address
 
◆ Willing to participate in all study components
 
◆ Willing to be followed-up for 6 months
 
◆ Self identifies as American Indian or Alaska Native
 
◆ Is a current smoker – self defined
 
	
 
◆ Planning to leave the college within next 6 months
 
◆ Medically ineligible as a result of screening questions
 

Medical Exclusion Criteria

For overall participation
 
 
◆ Medically ineligible as a result of screening questions
 
◆ Participant under the age of 18 years
 

For NRT (Patch, gum, lozenge):
 
 
• History of severe eczema or any serious skin problem if requested nicotine patch
 
• History of severe allergic reaction to the nicotine patch or other skin adhesives
 
• History of heart attack in the last 2 months
 
• Currently experiencing frequent angina or chest pain related to heart
 
• Currently experiencing signs and symptoms of peptic ulcer
 
• Currently receiving medications for rapid or irregular heart beat
 
• Currently experiencing signs and symptoms of severe, uncontrolled high blood pressure
 
 
For Chantix:
 
 
• Pregnant or breast feeding or planning to become pregnant in the next 6 months
 
• Currently using nicotine replacement therapy (NRT)
 
• History of suicide attempt in the past 12 months
 

- History of thoughts of suicide in the past 12 months
- History of thoughts of harming others in the past 12 months

For Zyban:

- Pregnant or breast feeding or planning to become pregnant in the next 6 months
- History of seizure disorder or head trauma
- History of severe allergic reaction to Zyban (also known as Wellbutrin, Bupropion)
- History of eating disorder, such as anorexia or bulimia, which is overeating and throwing up
- Currently taking Wellbutrin, Zyban or any other medications that contain bupropion

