## Measures

**Schedule of Assessments:** The table below represents our preliminary listing of outcome assessments, based on measures used for ANBL and preliminary discussions with community members. During year one of the project, we will work closely with our community partners to refine all measures and potentially add or subtract some of them. Our community partners will have final say on all measures to be used, including whether we use standard measures validated in other populations or modify for our community.

Measures Week	1	2	3	4	5	6	7	8	12	6 mo
Primary Outcome										
The primary endpoint for the study will be biochemically (salivary cotinine) verified point prevalence abstinence, defined as no smoking for the previous 7 days, at the 6-month follow-up. This definition is based on recent consensus statements from the Society for Research on Nicotine and Tobacco Subcommittee on Abstinence Measures.	X								X	X
Biochemical Validation	X								X	X
Pharmacotherapy Use		X	X	X	X	X	X	X	X	
Demographics Tribal affiliation, age, gender, marital status, income, year in school	X									
Smoking behavior										
Traditional use of tobacco	X	X	X	X	X	X	X	X	X	X
Smoking history (age of initiation)	X									
Quitting history (length of most recent quit attempt, number of quit attempts in the past year)	X									
Self-reported Smoking status (number of cigarettes/day)	X	X	X	X	X	X	X	X	X	X
Nicotine Dependence - The Fagerstrom Test of Nicotine Dependence will be used to measure nicotine dependence. 	X								X	X
Self-efficacy	X			X				X	X	X
Motivation	X			X				X	X	X
Environmental factors										
Household structure	X								X	X
Social support	X								X	X

Exposure to others who use tobacco in any form	X			X		X			X	X
Exposure to tobacco marketing	X			X		X			X	X
Psychosocial factors										
Depression using the CES-D, 10-item. 	X		X		X		X		X	X
Negative Affect from the Positive and Negative Affect Scale (PANAS) , 	X		X		X		X		X	X
Nicotine Withdrawal using the Minnesota Withdrawal Scale (MNWS) 	X		X		X		X		X	X
Craving using the Brief Questionnaire of Smoking Urges (QSU-Brief) , 	X		X		X		X			
Treatment Factors										
Satisfaction with interactive website					X				X	X
Satisfaction with session topics		X	X	X	X	X	X	X	X	
Satisfaction with session educational materials	X	X	X	X	X	X	X	X	X	

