### Phase 3: Data Analysis and Dissemination

The objectives of this phase are 1) to conduct data analysis and 2) to disseminate the program.

In Year 5, we will complete post-intervention assessments, data analyses and report writing.

Process and outcome data will be presented at scientific conferences and manuscripts will be submitted to peer-reviewed scientific journals. Ultimately, we envision that **I-ANBL**, if efficacious, could be disseminated and

used as a culturally tailored smoking cessation intervention that could be adopted across different tribal colleges.

**Sample Size and Power:** The primary endpoint will be cotinine verified 7-day point prevalence abstinence at Month 6. Per preliminary findings, we expect a 30% cessation rate in the **I-ANBL** arm and a 15% cessation rate in the **I-FV** arm. Using the chi-square test, and the assumptions above, 121 participants in each group will give us 80% power to detect this difference with a type I error rate of 5%.

Given retention rates from our earlier studies, we expect attrition rates to be approximately 20% over the 6 month study period. Therefore, we anticipate needing to enroll 300 participants at baseline in order to have 242 active participants at 6 months.

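### Two different definitions of current smoker govern entry, and neither is tied to the 7-day window of the primary endpoint

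*Protocol*

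**What the plan says.** **Who may enter.** Section IV (Eligibility) lists as an inclusion criterion "Is a current smoker – self defined". It gives no time window and no minimum consumption. Section V (Eligibility Requirements) describes the same population as "tribal college students who are current smokers (smoked at least 1 cigarette in the past 30 days".

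**What counts as success.** The Primary Aim is stated in terms of "7-day point prevalence abstinence (defined as no cigarettes in the past 7 days, biochemically verified) rates at 6 months". The Measures table repeats it as "verified point prevalence abstinence, defined as no smoking for the previous 7 days, at the 6-month follow-up". The sample-size paragraph and the primary hypothesis use the same 7-day endpoint. (The Design Overview names continuous abstinence instead; that is a separate inconsistency, not pursued here.)

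**What is known at entry.** Smoking status is reviewed at the telephone screen and saliva is taken at the in-person visit. The Measures table marks the primary-outcome, biochemical-validation and cigarettes-per-day rows at week 1. Nothing makes 7-day smoking or a cotinine result a condition of entry.

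**What the design presupposes.** Section III (Risks) treats every participant as someone who is going to quit, and the description of Internet Sessions 2-8 sets the second session as the common quit date.

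**Planned rates.** The sample-size paragraph says "Per preliminary findings, we expect a 30% cessation rate in the" I-ANBL arm and 15% in the I-FV arm, and that "121 participants in each group will give us 80% power to detect this difference with a type I error rate of 5" per cent.

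**The concern.** The two entry rules give research assistants different answers. A self-described smoker whose last cigarette was six weeks ago passes the inclusion table and fails Eligibility Requirements. A student who smoked once in the past 30 days but does not regard themselves as a smoker does the reverse.

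Both rules also leave a gap against the endpoint. A student who last smoked 8 to 30 days before entry satisfies the 30-day rule and, on the day of randomisation, already satisfies the self-report part of the outcome. If that student is abstinent at 6 months with confirming cotinine, the result is a success, although it may reflect a state present at entry.

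At stake are what a 6-month success means and, on one reading of the planning rates, some dilution of the difference between arms.

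**Working it through.** **1. The plan's own figure.** Inputs from Sample Size and Power: 0.30 against 0.15, 121 per arm, 5% type I error (taken as two-sided), chi-square test. With p̄ = 0.225, power = Φ{[0.15 − 1.96·√(2·0.225·0.775/121)] / √[(0.30·0.70 + 0.15·0.85)/121]} = 80.2%. The same formula solved for 80% power gives 121 per arm. The stated size reproduces.

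**2. Assumptions that the protocol does not supply.** Let s be the share of analysed participants already 7-day abstinent at entry, and r their abstinence rate at 6 months. I take s = 1%, 2% and 5%, and r from 0.30 to 0.90. The protocol remarks that "AI/AN smokers are lighter smokers than white smokers in the U.S", but this does not say how many smoke less than weekly.

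**3. Power if 30% and 15% are whole-arm rates.** These students are already inside the two rates. Power is 80.2% at any s.

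**4. Power if 30% and 15% describe recent smokers only.** With no effect in the already-abstinent students, the arm rates become (1−s)·0.30 + s·r and (1−s)·0.15 + s·r. With the same 15-point effect in them, I-ANBL uses r + 0.15 in place of r, and r runs from 0.30 to 0.70 (0.45 against 0.30, up to 0.85 against 0.70).

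| s | Power, no effect in these students | Power, same 15-point effect |
|---|---|---|
| 1% | 78.5 to 79.3% | 79.5 to 80.0% |
| 2% | 76.9 to 78.3% | 78.8 to 79.8% |
| 5% | 71.9 to 75.5% | 76.9 to 79.2% |

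Example: s = 5%, r = 0.90, no effect gives 0.95·0.30 + 0.05·0.90 = 0.330 against 0.95·0.15 + 0.05·0.90 = 0.1875, and power 71.9%.

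**5. Successes that could reflect abstinence present at entry.** With whole-arm rates, the share is at most s·r/0.15 in I-FV and s·r/0.30 in I-ANBL. At s = 2% this is 4 to 12% and 2 to 6%; at s = 5% it is 10 to 30% and 5 to 15%. These are upper bounds. They count every such entrant who is abstinent at 6 months, including one who smoked on after entry and then quit.

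**6. What adjustment recovers.** A stratified Mantel-Haenszel test on baseline 7-day status stands in for the covariate (60,000 simulations, s = 5%, no effect in these students). It gives 76.2% power against 76.2% unstratified at r = 0.30, and 77.7% against 72.4% at r = 0.90. Restricting to recent smokers leaves about 121·0.95 = 115 per arm and 78.1% power.

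**7. Recruitment room.** The Eligibility Requirements table gives 1,200·0.40·0.50·0.80 = 192 per year. Over 3 years that is at most 576, fewer if the same students recur between years, against a target of 300.

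**The case against.** The strongest reply is that the endpoint is a status at 6 months, not a change from baseline. Randomisation spreads already-abstinent students over both arms in expectation, and I-ANBL also covers staying quit, so sustained abstinence is a legitimate outcome. That stands: the comparison is valid as defined.

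A reader might infer that the trial is underpowered. The text does not support this. The sample-size paragraph attaches each rate to an arm, and an arm is everyone randomised to it; on that plain reading power is unchanged. The 30% matches a pilot result ("The six month smoking abstinence rates are approximately 30% with ANBL in combination with varenicline"). That pilot's smoking criterion is not given, which leaves the recent-smoker reading open but does not establish it.

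A reader might also take the shares in step 5 as the proportion of successes that are not cessation. They are not. A student who smokes every ten to twenty days has not quit at entry and may truly quit later. Because the programme is built for people about to quit, a large s is also less likely.

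Finally, covariates and sensitivity analyses are commonly left to a statistical analysis plan, so their absence here is not a fault. What the reply does not remove is the conflict between two entry rules, which fixes who is enrolled and belongs in the protocol.

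**Conclusion.** The contradiction between the two definitions is certain and needs no assumption. So is the mismatch with the 7-day endpoint: neither rule stops a student already 7-day abstinent by self-report from being randomised and later counted in a cessation rate.

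The consequences are modest and uncertain. There is no bias towards either arm. Power stays at 80.2% if the planning rates are whole-arm rates. If they describe recent smokers, it is about 77 to 80% at an assumed 1 to 2% share and 72 to 79% at an assumed 5% share. How many successes would reflect abstinence present at entry is unknown.

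The point therefore warrants a correction of wording and a small addition to the analysis, not a new sample size.

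**What to change.** (a) State one definition of current smoker, in the same words, in Section IV and in Eligibility Requirements.

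(b) Record 7-day smoking status, which the Measures table already allows for at baseline, before the arm is disclosed: at the telephone screen or at the start of the in-person visit. The timing matters because the research assistant brings the assignments to that visit. Enter this status as a covariate in the primary logistic regression, and add a sensitivity analysis restricted to those who smoked in the 7 days before assignment. Smoking history is at present only an exploratory covariate.

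Requiring a cigarette in the past 7 days for entry is an option for the investigators and the community advisory board, not a necessary correction. It would lose some intermittent smokers and sits uneasily with the community's wish for broader entry, voiced about other tobacco products. If 2%, 5% or 10% of otherwise eligible students failed the rule, enrolling 300 would take about 306 (300/0.98), 316 (300/0.95) or 333 (300/0.90). The recruitment table suggests some room for this.

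The cost of (a) and (b) is a fixed moment for one question and one extra analysis. The gain in power from the covariate is small: none at r = 0.30 and about 5 points at r = 0.90, with a 5% share and no effect in these students. The main benefit is a clear meaning for the endpoint.
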